10.2. DEFINITION OF STUDY POPULATIONS

Dose escalation part

- Population assessable for DLT assessment :
 - Patients assessable for the DLT assessment must fulfill all the following criteria:
 - Completed the DLT assessment period
 - Received concomitantly at least seven consecutive days of Olaparib and radiotherapy treatment (any dose) at least once.
 - Unless they develop a DLT, the following patients will not be included in the population assessable for DLT :
 - Patients who did not receive radiotherapy
 - Patients who did not receive nor Olaparib;
 - Patients who did not complete the full DLT evaluation period and goes off-treatment for reasons other than toxicity;

These patients will be replaced to reach the sample size requirement for dose escalation study.

- Safety population: patients who received radiotherapy or olaparib, at least once, irrespective of the dose. .

Expansion cohort

- Eligible population: All patients included without major violation of eligibility criteria.
- Population eligible and assessable for the primary endpoint : patients who fulfill all criteria below:
 - Eligible patients
 - Received concomitantly at least seven consecutive days of Olaparib and radiotherapy treatment (any dose) at least once.
 - at least one disease measurement recorded not less than eight weeks after treatment onset.

The following patients will also be included in the population evaluable for efficacy; they will be considered as failures for the primary endpoint (i.e. progressive disease at 6 months) and not be replaced in the efficacy analysis:

- Eligible patients withdrawn due to drug-related toxicity without any tumor assessments after the start of study treatment.
- Eligible patients withdrawn due to significant clinical deterioration of unknown reason, hypersensitivity reactions, or unrelated AEs without any tumor assessments after the start of study treatment.
- ***Replacement of patients: patients who do not comply with the definition of the population "eligible and assessable for the primary endpoint" will be replaced to reach the sample size requirement for expansion cohort.***
- Safety population: patients who receive at least one administration of Olaparib, or radiotherapy treatment at least once.

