APPENDIX 3: EVALUATION OF RESPONSE. THE RECIST

Response and progression will be evaluated in this study using the new international criteria proposed by the revised Response Evaluation Criteria in Solid Tumors (RECIST) guideline (version 1.1) [Eur J Ca 45:228-247, 2009]. Changes in only the largest diameter (unidimensional measurement) of the tumor lesions are used in the RECIST criteria.

DEFINITIONS

Evaluable for toxicity: All patients will be evaluable for toxicity from the time of their first treatment with study drugs.

Evaluable for objective response: Only those patients who have measurable disease present at baseline, have received at least one cycle of therapy, and have had their disease re-evaluated will be considered evaluable for response. These patients will have their response classified according to the definitions stated below. (Note: Patients who exhibit objective disease progression prior to the end of cycle 1 will also be considered evaluable.)

DISEASE PARAMETERS

Measurable disease. Measurable lesions are defined as those that can be accurately measured in at least one dimension (longest diameter to be recorded) as ≥ 20 mm by chest x-ray, as ≥ 10 mm with CT scan, or ≥ 10 mm with calipers by clinical exam. All tumor measurements must be recorded in millimeters (or decimal fractions of centimeters).

Note: Tumor lesions that are situated in a previously irradiated area are not considered measurable.

Malignant lymph nodes. To be considered pathologically enlarged and measurable, a lymph node must be ≥ 15 mm in short axis when assessed by CT scan (CT scan slice thickness recommended to be no greater than 5 mm). At baseline and in follow-up, only the short axis will be measured and followed.

Non-measurable disease. All other lesions (or sites of disease), including small lesions (longest diameter < 10 mm or pathological lymph nodes with ≥ 10 to < 15 mm short axis), are considered non-measurable disease. Bone lesions, leptomeningeal disease, ascites, pleural/pericardial effusions, lymphangitis cutis/pulmonitis, inflammatory breast disease, and abdominal masses (not followed by CT or MRI), are considered as non-measurable.

Note: Cystic lesions that meet the criteria for radiographically defined simple cysts should not be considered as malignant lesions (neither measurable nor non-measurable) since they are, by definition, simple cysts.

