#### **4.2.11 EFFICACY: Response, Progression and Survival**

- Table 14.1. Frequency distribution of objective response on population evaluable for efficacy
- Table 14.2. Frequency distribution of 6-month non-progression on population evaluable for efficacy

- Table 14.3. Frequency distribution of progression at one year on population evaluable for efficacy
- Table 14.4. Frequency distribution of deaths at one year on population evaluable for efficacy
- Table 14.5. Median follow-up time on population evaluable for efficacy– Life table
- Table 14.6. Median progression-free survival on population evaluable for efficacy – Life table
- Table 14.7. Median overall survival on population evaluable for efficacy – Life table

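### Appendix 3 and section 10.2 give different denominators for tumour response, and dose escalation has only the Appendix 3 rule, which can raise response proportions where patients leave unscanned

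*Protocol*

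**What the plan says.** **Appendix 3 (Definitions).** Evaluable for objective response are "Only those patients who have measurable disease present at baseline, have received at least one cycle of therapy, and have had their disease re-evaluated". One exception is added: "Patients who exhibit objective disease progression prior to the end of cycle 1 will also be considered evaluable". Cycle labels appear in the pharmacokinetic schedule (section 17.1.1: C1D1, C1D8, C1D28), but no cycle length is given, and section 3.4.1 describes olaparib as continuous.

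**Section 10.2, expansion cohort (repeated in SAP 2.1.2).** The assessable set needs eligibility, seven consecutive days of both treatments together, and "at least one disease measurement recorded not less than eight weeks after treatment onset". Two further groups are brought in. The first covers patients who stop because of toxicity: "Eligible patients withdrawn due to drug-related toxicity without any tumor assessments after the start of study treatment". The second covers those who stop for several other medical reasons, again unscanned: "Eligible patients withdrawn due to significant clinical deterioration of unknown reason, hypersensitivity reactions, or unrelated AEs without any tumor assessments".

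Of both groups the text says "they will be considered as failures for the primary endpoint (i.e. progressive disease at 6 months) and not be replaced in the efficacy analysis". Anyone else outside the definition "will be replaced to reach the sample size requirement for expansion cohort".

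**SAP 4.2.11.** Table 14.1 is the "Frequency distribution of objective response on population evaluable for efficacy". Table 14.2 puts 6-month non-progression on the same named set.

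**Dose escalation.** Section 10.2 and SAP 2.1.1 define only a DLT-assessable and a safety population. Yet section 10.3 and SAP 3.1.1 report efficacy as proportions at each dose level, and SAP Table 1.4 counts efficacy-evaluable patients by dose level.

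**The concern.** A patient who stops early for toxicity and is never re-imaged is outside the Appendix 3 denominator but inside the 10.2 set as a failure. If response is computed by one rule and non-progression by the other, the two rates in the same cohort rest on different patients, and treatment failures drop out of the response rate.

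Dose escalation is more exposed, because no efficacy population competes with Appendix 3. Response is reported by dose level on a handful of patients each. If more patients leave before re-imaging at one level than at another, that level's response proportion rises for a reason unrelated to activity.

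The one-cycle condition adds a separate problem. Without a cycle length, two analysts could apply it differently.

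**Working it through.** **1. Inputs.** From section 10.1: 14 assessable patients in the expansion cohort, 24 in dose escalation, four dose levels. The documents give no counts of responders (r), patients with stable disease (s) or unscanned 10.2 failures (f). These are assumed: r from 1 to 8, f from 0 to 3, all possible s.

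**2. The plan's own figure.** Gehan stage 1 needs the smallest n with (1 − 0.20)^n ≤ 0.05. Since 0.8^13 = 0.0550 and 0.8^14 = 0.0440, n = 14, as stated.

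**3. The two rules side by side (expansion cohort).**

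| Patient | Appendix 3 | Section 10.2 |
|---|---|---|
| Never re-scanned; left for drug toxicity, unexplained deterioration, hypersensitivity or unrelated adverse event | out | in, failure |
| Never re-scanned; left for another reason, such as refusal | out | out, replaced |
| Progression measured only before week 8 | in, non-responder | out, replaced |

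The rules differ in the first and third rows, in opposite directions.

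**4. Unscanned failures.** Appendix 3 gives r/(14 − f); 10.2 with failures scored as non-responders gives r/14.

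| f | r = 3 | r = 5 |
|---|---|---|
| 0 (same as 10.2) | 3/14 = 21.4% | 5/14 = 35.7% |
| 1 | 3/13 = 23.1% | 5/13 = 38.5% |
| 2 | 3/12 = 25.0% | 5/12 = 41.7% |
| 3 | 3/11 = 27.3% | 5/11 = 45.5% |

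For scale, the exact 95% interval for 3/14 is 4.7% to 50.8%, and for 3/12 it is 5.5% to 57.2%.

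**5. When 6-month response exceeds 6-month non-progression.** This needs r/(14 − f) > (r + s)/14, that is, r·f > s·(14 − f). With r = 5:
- f = 1: 5 > 13s, so only s = 0.
- f = 2: 10 > 12s, so only s = 0.
- f = 3: 15 > 11s, so s = 0 or 1.

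Across r = 1 to 8 and f ≤ 3, the most stable disease that still allows it is s = 2, at r = 8 and f = 3 (24 > 22).

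**6. The opposite direction.** With r = 3 and f = 0, one patient whose progression was measured only before week 8 gives 3/15 = 20.0% under Appendix 3, and two give 3/16 = 18.8%, against 21.4% under 10.2. Two such patients and two unscanned failures cancel: 3/(14 − 2 + 2) = 3/14.

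**7. Dose escalation.** The planned size averages 24/4 = 6 patients per level, although adaptive allocation will not be even. With 6 treated, 2 responders and 2 leaving unscanned (assumed), Appendix 3 gives 2/4 = 50%. Counting all treated patients gives 2/6 = 33%.

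**8. Can patients leave unscanned?** Section 5.5 schedules MRI at weeks 12 and 24, with CT every 8 weeks for metastatic disease. Section 5.6 asks for imaging at the end-of-treatment visit, unless progression is confirmed or a new treatment has begun. That lowers the number of unscanned patients but does not exclude them.

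**The case against.** The best defence is that the SAP already settles the expansion cohort. Tables 14.1 and 14.2 share one named population, and section 10.2 uses that name for the set containing the failures. No analysis section or table invokes the Appendix 3 set. On this view the paragraph is an unreconciled appendix text with no effect. The response endpoints are also secondary and descriptive, without p-values.

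Much of this stands. Following the SAP table list, with failures scored as non-responders, removes the discrepancy in the expansion cohort. Two gaps remain:
- Section 10.2 calls these patients failures for the primary endpoint only. Nothing says how they score for objective or best response, and missing data are not imputed. Appendix 3 itself asks the analysis plan to settle how missing assessments enter response determination; the SAP has no such rule. It builds indicators for eligibility, DLT and safety but none for efficacy, and its 6-month response entry in 3.2.2.1 ends in a count with no denominator.
- The defence does not reach dose escalation, where the table label refers to a population that is not defined. The heading of section 8.2 limits efficacy to the expansion cohort, but sections 2.2.1, 9.1 and 10.3 include it for escalation.

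A reader might go further and infer that the response rate is inflated as a matter of fact, or that 10.2 counts every unscanned patient as a failure. The documents support neither. The first depends on applying Appendix 3 against the SAP table list, and on few early progressions. The second overlooks that 10.2 replaces patients who leave for unlisted reasons, so both rules drop them.

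**Conclusion.** The point holds in a limited form. The protocol contains two incompatible evaluability rules for response, one resting on an undefined unit. In the expansion cohort the SAP points to the right set but leaves the scoring of the unscanned failures open. In dose escalation the only stated rule is one that can raise response proportions at levels where more patients leave unscanned.

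In the expansion cohort, applying Appendix 3 would move 5 responders from 35.7% to between 38.5% and 45.5% for 1 to 3 unscanned failures. That is 2.7 to 9.7 percentage points, small beside the sampling uncertainty. At a dose level of 6 the illustration moves 33% to 50%. All of these rest on assumed counts, and the expansion figures also assume no patient with progression measured only before week 8; such patients pull the rate down.

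A response rate above the non-progression rate is possible but is a corner case. It concerns 6-month response only and needs almost no stable disease. Best objective response under treatment is no evidence of a fault here: a responder can progress before 6 months, so that rate can exceed 6-month non-progression on any single denominator. The go rule, at least one non-progression among 14, uses the 10.2 set and does not change.

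**What to change.** 1. Remove the paragraph on evaluability for objective response from Appendix 3, or align it with section 10.2. Either way, drop the one-cycle condition or define a cycle. If the paragraph is deleted, its early-progression note goes too, so state how a patient whose progression is measured only before week 8 is handled.
2. State in sections 10.2 and 10.3 and in the SAP that all response endpoints in the expansion cohort use the 10.2 efficacy population, with the listed unassessed failures counted as non-responders. Add an efficacy-evaluable indicator to the SAP and name the denominator in 3.2.2.
3. Define an efficacy population for dose escalation, for example eligible patients who started treatment. Count members without a post-baseline assessment as non-responders and retain early objective progression. Citing 10.2 is not enough, because it has no such set for this part.

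The cost is wording in one appendix, two protocol sections and the SAP, with no new data. Reported response rates may be slightly lower. It is best done before the analysis, since at these sample sizes each exclusion visibly moves a rate.

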APPENDIX 4: SERIOUS ADVERSE EVENT NOTIFICATION FORM

SERIOUS ADVERSE EVENT NOTIFICATION FORM

To be faxed to the vigilance unit - N° [name]

PROTOCOL: RADIO SARP	EUDRACT/ID-RCB N° 2015-003722-13	COUNTRY: France
SPONSOR IDENTIFICATION N°:	INVESTIGATOR SITE :	SITE N°:
DATE OF THIS REPORT:	INITIAL REPORT 	FOLLOW-UP REPORT N°
		FINAL REPORT 

1. PARTICIPANT IDENTIFICATION

IDENTIFICATION N°: | | | | | DATE OF INCLUSION: | | | | | TREATMENT ARM: | | | | | DOSE LEVEL (PHASE I STUDY): | | | | |
 SURNAME (1 LETTER): | | | | | 1ST NAME (1 LETTER): | | | | | AGE AT THE TIME OF THE EVENT (YEARS-OLD): | | | | |
 GENDER: F ☐ M ☐ HEIGHT (CM): | | | | | WEIGHT (KG): | | | | | BODY SURFACE AREA (M²): | | | | |
 DISEASE UNDER STUDY (diagnosis, localization and metastases site if applicable): | | | | |

2. INFORMATION ON EVENT

DATE OF INVESTIGATOR AWARENESS OF SAE: | | | | | DATE OF EVENT ONSET: | | | | |
 DATE OF SERIOUSNESS ONSET: | | | | | TOXICITY (NCI-CTC GRADE): 1 ☐ 2 ☐ 3 ☐ 4 ☐ 5 ☐
 DIAGNOSIS OR MAIN SYMPTOM. ONLY ONE DIAGNOSIS OR ONE SYMPTOM (except for linked symptoms): | | | | |

DESCRIBE EVENT AND TREATMENT GIVEN (INCLUDING RELEVANT TEST/LAB DATA): | | | | |

3. SERIOUSNESS CRITERIA

☐ DEATH, DATE OF DEATH: | | | | |
☐ LIFE-THREATENING
☐ REQUIRING or ☐ PROLONGING HOSPITALIZATION:
 DATE OF ADMISSION: | | | | |
☐ PERSISTENT/SIGNIFICANT DISABILITY/INCAPACITY
☐ CONGENITAL ANOMALY/BIRTH DEFECT
☐ MEDICALLY RELEVANT

ADVERSE EVENT OF SPECIAL INTEREST (AESI) Yes ☐ No ☐
 (SEE PROTOCOL)

SPECIAL CONSIDERATIONS Yes ☐ No ☐
 (SEE PROTOCOL)

☐ SERIOUS (COMPLETE SECTION 3) OR ☐ NOT SERIOUS

4. OUTCOME

☐ ONGOING EVENT ☐ UNKNOWN OUTCOME
☐ RECOVERED WITHOUT SEQUELAE, DATE: | | | | |
☐ RECOVERED WITH SEQUELAE, DATE: | | | | |
 SPECIFY SEQUELAE: | | | | |

☐ DEATH RELATED TO THIS EVENT, DATE: | | | | |
☐ DEATH UNRELATED TO THIS EVENT, DATE: | | | | |
 CAUSE OF DEATH: | | | | |
 OR CAUSE UNKNOWN ☐
 PLEASE, SPECIFY ABOVE THE OUTCOME OF THE EVENT AT THE TIME OF UNRELATED DEATH

☐ AUTOPSY: Yes ☐ No ☐ UNKNOWN ☐

If PATIENT WAS HOSPITALIZED: DATE OF END OF HOSPITALIZATION: | | | | |
 OR PATIENT STILL HOSPITALIZED AT TIME OF THIS REPORT ☐

FOR IMP TRIALS > COMPLETE SECTION 5 FOR RADIOTHERAPY TRIALS > COMPLETE SECTION 6

5. IMP (INVESTIGATIONAL MEDICINAL PRODUCT(S))

TICK IF NA ☐

INVESTIGATIONAL PRODUCT(S) Indicate the International Common Denomination of the IMP & other combined	ROUTE	SAE CYCLE NUMBER	DATES		DOSE & UNITS	
			DATE OF FIRST ADMINISTRATION/USE (1 ST DAY OF 1 ST CYCLE)	DATE OF LAST ADMINISTRATION/USE BEFORE SAE	LAST DOSE ADMINISTERED BEFORE SAE	CUMULATIVE DOSE SINCE THE 1 ST ADMINISTRATION
1						
2						
3						
4						
5						

UNBLINDING: Yes ☐ No ☐ NA ☐

HAS ONE (OR SEVERAL) INVESTIGATIONAL PRODUCT(S) BEEN STOPPED?

☐ Yes N° | | | | | N° | | | | | Date: | | | | | ☐ No ☐ NA

IF YES, SPECIFY: ☐ TEMPORALLY ☐ DEFINITELY

DID THE EVENT DISAPPEAR AFTER INVESTIGATIONAL PRODUCT(S) IS STOPPED?

☐ Yes ☐ No ☐ NA

HAS ONE (OR SEVERAL) INVESTIGATIONAL PRODUCT(S) BEEN REINTRODUCED?

☐ Yes N° | | | | | N° | | | | | N° | | | | | ☐ No ☐ NA

IF YES, SPECIFY: Date: | | | | | Dose: | | | | |

DID THE EVENT REAPPEAR AFTER INVESTIGATIONAL PRODUCT(S) REINTRODUCTION?

☐ Yes ☐ No ☐ NA

PROTOCOL : RADIO SARP		EUDRACT/ID-RCB N°: 2015-003722-13		COUNTRY: France
SPONSOR IDENTIFICATION N°:		INVESTIGATOR SITE :		SITE N°:
DATE OF THIS REPORT:		INITIAL REPORT 	FOLLOW-UP REPORT N°	FINAL REPORT 
INCLUSION N°:		SURNAME (1 LETTER): 1 ST NAME (1 LETTER): Age (YEARS OLD):		

9. ASSESSMENT: IN YOUR OPINION (INVESTIGATOR), THIS EVENT IS RELATED TO:

- ☐ IMP (INVESTIGATIONAL MEDICINAL PRODUCT(S))
☐ INVESTIGATIONAL RADIOTHERAPY

IF NOT RELATED TO INVESTIGATIONAL MP / RADIOTHERAPY, PLEASE SPECIFY:

- ☐ PROTOCOL/STUDY PROCEDURE, SPECIFY:
☐ DISEASE UNDER STUDY, SPECIFY:
☐ CONCOMITANT TREATMENT(S), SPECIFY:
☐ CONCOMITANT DISEASE(S), SPECIFY:
☐ OTHER, SPECIFY:

10. SAE NOTIFIED BY:

NAME:
 FUNCTION:
 ADDRESS:
 PHONE: FAX:
 E-MAIL:
 DATE | | / | | / | | | |
 SIGNATURE:

INVESTIGATOR

NAME:
 DEPARTMENT:
 DATE | | / | | / | | | |
 SIGNATURE:

SPONSOR ONLY (DO NOT FULFIL THIS PART)

TYPE OF REPORT: ☐ SAE ☐ ADVERSE EVENT OF SPECIAL INTEREST ☐ SPECIAL CONSIDERATIONS

SPONSOR IDENTIFICATION NUMBER:

DATE OF RECEIPT: | | / | | / | | | |

ASSESSMENT:

- 1 ☐ INVESTIGATIONAL MP
 2 ☐ INVESTIGATIONAL RADIOTHERAPY

UNEXPECTED: YES ☐ NO ☐

REFERENCE SAFETY INFORMATION (TYPE, VERSION):

IF NOT RELATED TO EITHER 1 OR 2, PLEASE SPECIFY

- 3 ☐ PROTOCOL/STUDY PROCEDURE, SPECIFY:
 4 ☐ DISEASE UNDER STUDY
 5 ☐ CONCOMITANT TREATMENT(S) SPECIFY:
 6 ☐ CONCOMITANT DISEASE(S), SPECIFY
 7 ☐ OTHER, SPECIFY

DATE | | / | | / | | | | NAME SIGNATURE:

APPENDIX 6: ACCEPTABLE BIRTH CONTROL METHODS

Olaparib is regarded as a compound with medium/high foetal risk.

Women of childbearing potential and their partners, who are sexually active, must agree to the use of TWO highly effective forms of contraception in combination [as listed below], throughout the period of taking study treatment and for at least 1 month after last dose of study drug(s), or they must totally/truly abstain from any form of sexual intercourse (see below).

<include if recruiting male patients> Male patients and their partners, who are sexually active and of childbearing potential, must agree to the use of TWO highly effective forms of contraception in combination [as listed below], throughout the period of taking study treatment and for 3 months after last dose of study drug(s) due to the unknown effects of the study drug on the sperm, or they must totally/truly abstain from any form of sexual intercourse (see below). Male patients should not donate sperm throughout the period of taking study treatment and for 3 months following the last dose of study drug(s).

Acceptable Non-hormonal birth control methods include:

- Total/true abstinence: When the patient refrains from any form of sexual intercourse and this is in line with their usual and/or preferred lifestyle; this must continue for the total duration of the study treatment and for at least 1 month (for female patients) or at least 3 months (for male patients) after the last dose of study treatment. Periodic abstinence (eg, calendar ovulation, symptothermal, post-ovulation methods, or declaration of abstinence solely for the duration of a trial) and withdrawal are not acceptable methods of contraception.
- Vasectomised sexual partner PLUS male condom (with participant assurance that partner received post-vasectomy confirmation of azoospermia).
- Tubal occlusion PLUS male condom.
- Intrauterine device (provided coils are copper-banded) PLUS male condom

Acceptable hormonal methods:

- Mini pill PLUS male condom: Progesterone-based oral contraceptive pill using desogestrel. Cerazette (Merck Sharp & Dohme) is currently the only highly efficacious progesterone-based pill available.
- Combined pill PLUS male condom: Normal and low-dose combined oral pills.
- Injection PLUS male condom: Medroxyprogesterone injection (eg, Depo-Provera [Pfizer]).
- Implants PLUS male condom: Etonorgestrel-releasing implants (eg, Nexplanon [Merck Sharp & Dohme]).
- Patch PLUS male condom: Norelgestromin/ethinyl estradiol transdermal system (eg, Xulane).
- Intravaginal device (eg, ethinyl estradiol-/etonogestrel-releasing intravaginal devices such as NuvaRing [Merck Sharp & Dohme]) PLUS male condom.
- Levonorgestrel-releasing intrauterine system (eg, Mirena [Bayer]) PLUS male condom.

APPENDIX 7: MUSKULOSKELETAL TUMOR SOCIETY FUNCTIONAL FORM

SCORE	PAIN	FUNCTION	EMOTIONAL	SUPPORTS	WALKING	GAIT	Final Patient
5	No pain	No restriction	Enthused	None	Unlimited	Normal	Score of FUNCTIONAL EVALUATION
4	Intermediate	Intermediate	Intermediate	Intermediate	Intermediate	Intermediate	
3	Modest/Non-disabling	Recreational restriction	Satisfied	Brace	Limited	Minor cosmetic	
2	Intermediate	Intermediate	Intermediate	Intermediate	Intermediate	Intermediate	
1	Moderate/Disabling	Partial restriction	Accepts	One cane or crutch	Inside only	Major cosmetic	
0	Severe disabling	Total restriction	Dislikes	Two canes or crutches	Not independent	Major handicap	
Patient score

**SPONSOR**

**INSTITUT BERGONIE**

# 1 STUDY PROTOCOL (SUMMARY)

## 1.1 SYNOPSIS

Title of the study	A phase Ib study of Olaparib with concomitant radiotherapy in locally advanced/unresectable soft-tissue sarcoma
Abbreviation of the trial	RADIOSARP
Sponsor Identification	Institut Bergonié, Regional Comprehensive Cancer Center
Coordinating Investigator	Doctor [name] Department of Radiotherapy
Number of investigational sites planned	6 centres: - Institut Bergonié, Bordeaux - Centre Léon Bérard, Lyon - IUCT Oncopôle, Toulouse - Institut Gustave Roussy, Villejuif - Institut du Cancer, Montpellier - Centre Oscar Lambret, Lille
Number of patients	41 patients
Duration of the study	Planned enrollment period: 24 months Treatment duration: Radiotherapy over a period of 6.5 weeks. Olaparib will be started one week before the start of radiotherapy and will be continued until the last day of radiotherapy. Beyond this period, Olaparib could be continued at the investigator's discretion until progression. Follow-up: at least 1 year Study period: 3 years
Medical conditions	Adult patients with locally advanced/unresectable soft-tissue sarcoma
Objectives	
Primary objective
 
PHASE 1 TRIAL To establish the recommended phase II dose (RP2D), the maximum tolerated dose (MTD), the safety profile and the dose limiting toxicities (DLT) of Olaparib given with concomitant radiotherapy in patients with locally advanced/unresectable soft-tissue sarcoma.
 
EXPANSION COHORTS To determine preliminary signs of anti-tumor activity of Olaparib given with concomitant radiotherapy in patients with locally advanced/unresectable soft-tissue sarcoma in terms of 6-month non-progression (complete response, partial response, stable disease as per RECIST v1.1) after centralized radiological review.
 
Secondary objectives

	
DOSE ESCALATION PART PHASE 1 TRIAL:
 
 
- Preliminary signs of anti-tumor activity of Olaparib given with concomitant radiotherapy in terms of 6-month non-progression, 6-month objective response, objective response under treatment, best response under treatment, 1-year progression-free survival (PFS) and 1-year overall survival (OS).
 
- Functional assessment before and after treatment.
 
- Pharmacokinetics (PK) of Olaparib.
 
 
EXPANSION COHORT:
 
 
- Preliminary signs of anti-tumor activity of Olaparib given with concomitant radiotherapy in terms of 6-month objective response, objective response under treatment, best response under treatment, 1-year progression-free survival (PFS) and 1-year overall survival (OS).
 
- Toxicity profile of Olaparib given with concomitant radiotherapy.
 
- Functional assessment before and after treatment.
 
- Pharmacokinetics (PK) of Olaparib.
 
- Pharmacodynamics (translational research)
 


Study design
	
STUDY DESIGN
 
This is a multicenter, prospective phase Ib trial based on a dose escalation study design (3+3 traditional design) assessing four dose levels of Olaparib given with concomitant radiotherapy, followed by an expansion cohort.
 
DEFINITIONS
 
Dose-limiting toxicity (DLT)
 
A DLT is defined as an adverse event (AE) or laboratory abnormality that fulfills all the criteria below:
 
 
○ Occurs during the period of observation of DLTs defined as the period between the first day of treatment administration and up to 6 weeks after the end of radiotherapy.
 
○ Is considered to be at least possibly related to the treatment strategy (radiotherapy or Olaparib).
 
○ Is unrelated to disease, disease progression, inter-current illness, or concomitant medications.
 
○ Meets one of the criteria below, graded as outlined or according to NCI CTCAEv4.0 :             
 
▪ Any grade <math>\geq 3</math> musculoskeletal or cutaneous toxicity within the field of radiation:                 
 
• Occurring at a radiotherapy dose <math>< 30\text{Gy}</math>
 
• Occuring at a radiotherapy dose <math>\geq 30\text{Gy}</math> and without regression to a grade <math>\leq 2</math> in a time limit of 4 weeks
 
 
 
▪ Any non-hematological toxicity <math>\geq</math> grade 3 (except for nausea, vomiting, fatigue, alopecia and fever)
 
▪ Laboratory abnormality <math>\geq</math> grade 3 lasting <math>> 5</math> days (except for hyperglycaemia and changes in serum electrolytes/enzymes without clinical impact)
 
▪ Febrile neutropenia (absolute neutrophil count [ANC] <math>< 1.0 \times 10^9/\text{L}</math> and fever <math>\geq 38.5^\circ\text{C}</math>) and/or documented infection with ANC <math>< 1.0 \times 10^9/\text{L}</math>
 
 
 

- Grade 4 neutropenia (absolute neutrophil count < 500) lasting ≥ 7 days
- Grade 4 thrombocytopenia or bleeding requiring a platelet transfusion
- Any other toxicity grade ≥ 4
- Any other study drug related toxicity considered significant enough to be qualified as DLT in the opinion of the investigators after discussion with the sponsor.
- In addition, the following events in case they are related to the toxicity of the treatments will also be considered as DLT:
  - Interruption of radiotherapy for seven consecutive days or longer,
  - Interruption of Olaparib for 14 days or longer, whether this interruption happens on consecutive days or not.

A **DLT validation committee** will be consulted at each DLT notification for validation of the DLT status (see section 12.1.2).

